**Table 8: Adverse Event Classification Responsibilities**

What is classified?	Who classifies?	Classification Parameters
Relatedness	Investigator	Device, procedure, therapy
	Sponsor	Device, procedure, therapy, outside standard of care CIP procedure
Seriousness	Investigator	SAE, DD with SADE potential
	Sponsor	SAE, UADE (for all system or procedure related AEs), DD with SADE potential
Diagnosis	Investigator	Based on presenting signs and symptoms and other supporting data
	Sponsor	MedDRA term assigned based on the data provided by investigator

### ***11.2.2. Non-reportable and Unavoidable Adverse Events***

The following events do not qualify as adverse events and do not need to be reported:

- Documented pre-existing conditions without a change in the nature or severity of the condition
- Pre-planned hospitalizations for device change out (e.g. CRT, ICD, IPG)
- Appropriate cardiac device therapies received as a result of pre-existing arrhythmias
- SBP below 100 mmHg without producing symptoms suggestive of hypotension
- Unavoidable adverse events (**Table 9**)

The following table indicates the unavoidable adverse events that do not need to be reported. However, onset of any events listed in **Table 9** after the specified timeframes should be reported as an AE.

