- Pain – discomfort that can range from mild to severe that may occur peri- and/or post-procedure.
- Damage to one or both kidneys, loss of kidney function, and/or need to remove a kidney – perforation of kidney or an occlusion of blood flow to the kidney (*e.g.*, from stenosis or embolism) and/or reduction of glomerular filtration rate or need for nephrectomy. If severe enough, this could require dialysis.
- Renal artery aneurysm – localized weakening and ballooning of the renal artery from the interventional procedure or the delivery of RF energy.
- Renal artery stenosis – narrowing of the renal artery due to the interventional procedure or the delivery of RF energy.

- Arterial spasm or constriction – Acute or chronic narrowing of the renal artery lumen diameter at denervation locations due to arterial muscle contraction, local tissue contraction or local edema.
- Thermal injury to the vasculature or other structure from energy application - damage to an artery, vein, or other structure due to the delivery of energy.
- Hypertension – worsening high blood pressure.
- Hypotension – low blood pressure. BP reduction may occur too far and/or too quickly and may cause end organ hypoperfusion.
- Orthostatic hypotension – temporary reduction of blood pressure when going from lying to standing, coupled with symptoms (e.g., dizziness, light headedness).
- Hematuria – blood in urine.
- Hemorrhage – significant blood loss.
- Proteinuria – elevated levels of protein in urine.
- Electrolyte disturbances – an imbalance of the electrolytes (sodium, potassium).
- Skin burn – damage to the skin caused by energy conduction via the ground pad used with the Symplicity renal denervation system

The risks associated with not having a controlled blood pressure during the first four months include:

- Angina (chest pain, pressure or squeezing)
- Myocardial infarction (improper blood flow to the heart)
- Pulmonary edema (fluid accumulation in the air spaces of the lungs)
- Heart failure
- Stroke (disturbance in the blood supply to the brain)
- Atrial fibrillation (abnormal heart rhythm)
- Death

There are additional risks that could possibly be associated with the tests and procedures performed for the clinical study. These potential risks are described below.

The risks associated with subjects being off their antihypertensive medications during the washout period through three months post-procedure include:

- Death
- Stroke
- MI
- Angina
- Heart Failure
- Atrial fibrillation

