## **Serious Adverse Event (SAE): (ISO 14155 3.45)**

Adverse event that led to any of the following

- a) death,

b) serious deterioration in the health of the subject, users or other persons as defined by one or more of the following:

- 1) a life-threatening illness or injury, or
- 2) a permanent impairment of a body structure or a body function, including chronic diseases or
- 3) in-patient or prolonged hospitalization, or
- 4) medical or surgical intervention to prevent life-threatening illness or injury or permanent impairment to a body structure or a body function,

c) fetal distress, fetal death or a congenital abnormality or birth defect including physical or mental impairment.

*NOTE 1: Planned hospitalization for a pre-existing condition, or a procedure required by the CIP, without serious deterioration in health, is not considered a serious adverse event.*

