**Table 9: Unavoidable Adverse Events**

Event Description	Time Frame (hours) from the Renal Denervation Procedure
Anesthesia related nausea/vomiting	24
Low grade fever (<100°F or <37.8°C)	48
Mild to moderate bruising/ecchymosis (at insertion site)	168
Sleep problems (insomnia)	72
Back pain related to laying on table	72
Elevated blood pressure	During the procedure

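### Table 9 exempts listed mild peri-procedural events by time of onset, with no rule for one that persists or needs treatment, and with an unresolved conflict if one is serious

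*Protocol*

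**What the plan says.** Protocol section 11.2.2 opens its list of exemptions with "The following events do not qualify as adverse events and do not need to be reported". Table 9 events are the last item on that list. The sentence leading into the table "indicates the unavoidable adverse events that do not need to be reported. However, onset of any events listed in" that list is treated differently when it comes late: such an event, if it begins "after the specified timeframes should be reported as an AE". That is the only stated way back to reporting.

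Table 9 gives each event a limit in a column headed "Time Frame (hours) from the Renal Denervation Procedure". Some rows also restrict severity, site or cause. Fever must be below 37.8°C, bruising must be mild to moderate and at the insertion site, and the one pain entry is "Back pain related to laying on table".

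The surrounding rules are these:
- Section 11.1 defines an AE broadly, with no exception for expected events. It defines an SAE as "Adverse event that led to any of the following", followed by the seriousness criteria, which include prolonged hospitalization.
- Section 11.2.1 requires every AE to be reported through 6 months, whatever its cause or result.
- Table 6 lists SAEs for reporting and makes no exception for Table 9.
- Section 9.2 requires AEs to be followed until they resolve or stabilize, or until participation or the study ends.

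SAP section 7.8 restates the AE collection period and adds nothing on exempt events.

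**The concern.** An exemption for expected, short-lived effects of a catheter procedure is ordinary. It is justified because the event is minor and brief, so the test should look at how the event runs its course as well as when it begins. Section 11.2.2 tests only the beginning. Neither document says what happens when a listed event continues past its window, needs treatment or meets a seriousness criterion.

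This looks like an omission, because neighbouring exemptions in the same list do carry such conditions. A pre-existing condition is exempt only while its nature and severity are unchanged, and a low systolic pressure is exempt only if it causes no symptoms.

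At stake is the completeness of the AE record for a procedure whose safety the study is meant to confirm (protocol section 6.8). Sites may also handle the same event differently.

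**Working it through.** The plan gives no figure to reproduce. The check sets the passages side by side, with simple date arithmetic.

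**Step 1: windows against the visit schedule.** Inputs are Table 9 and the visit windows in Table 1.

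| Table 9 event | Limit | In days (hours / 24) | Restriction in the row |
|---|---|---|---|
| Nausea/vomiting | 24 h | 1 | anesthesia-related |
| Fever | 48 h | 2 | below 37.8°C |
| Insomnia | 72 h | 3 | none |
| Back pain | 72 h | 3 | from lying on the table |
| Bruising | 168 h | 7 | mild to moderate, insertion site |
| Elevated blood pressure | during the procedure | – | none |

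The first scheduled visit after discharge is at 2 weeks ± 3 days, that is, day 14 − 3 = 11 to day 14 + 3 = 17. The longest window closes on day 7. So any Table 9 complaint with early onset that is still present at that visit has outlasted its window by at least 11 − 7 = 4 days. On the onset rule it still need not be recorded.

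**Step 2: two cases under the onset rule.**
- Table-related back pain starts at hour 12 and lasts 3 weeks. Onset is inside 72 h, so it is not reportable.
- The same complaint starts at hour 73 and lasts one day. Onset is after 72 h, so it is reportable.

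The longer event is left out and the shorter one is recorded. The duty in section 9.2 to follow to resolution applies to AEs, so it does not reach the first case.

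**Step 3: a listed event that meets a seriousness criterion.** Two chains of reasoning are open.
- Starting from 11.1, the event is an untoward occurrence, hence an AE. With a serious consequence it is an SAE, and Table 6 requires it to be reported.
- Starting from 11.2.2, the event is not an AE. The SAE definition begins from an AE, so neither Table 6 nor 11.2.1 is engaged.

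The protocol does not say which provision prevails. Sections 11.2.1 and Table 6 do not settle it, because both presuppose the AE status that 11.2.2 removes.

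**Step 4: which outputs are affected.** I compared Table 9 with the endpoint lists in protocol section 4.2.2 and SAP section 7.7.1. No Table 9 item is a component of the composite or one of the other safety endpoints. The effect is confined to AE listings and tabulations.

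**The case against.** The case against is substantial, and much of it stands.

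**The exemption is narrower than it first looks.** A reader might infer that post-procedure pain, fever or bruising in general is exempt by onset alone. It is not. Fever of 37.8°C or more, severe bruising and pain from any other cause are reportable whenever they start, and an event that worsens beyond its row leaves the exemption. In particular, the pain that section 10.1 lists among the unquantified denervation risks, described as "discomfort that can range from mild to severe that may occur peri- and/or post-procedure", is not in Table 9. This stands.

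**Important complications are not hidden.** A reader might infer that infection or retroperitoneal bleeding escapes because it first shows as fever or back pain. The documents do not support that. Under Table 8 the investigator makes the diagnosis, and neither diagnosis is on the list. Access-site complications that need surgical repair, an interventional procedure, thrombin injection or more than 2 units of red cells are vascular complications under section 16.4 and are adjudicated as part of the composite. This also stands.

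**Serious events must be reported anyway.** This stands only in part. Table 6 and section 11.2.1 point that way, but both depend on AE status. A reader might infer the opposite, that a serious Table 9 event can never be an AE. That is equally unsupported, because the provisions conflict and neither is given precedence.

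**The column heading may end the exemption when the window closes.** It does not say whether the hours limit onset or the whole exemption. The sentence above the table, however, speaks only of onset. The ambiguity is itself a reason to clarify.

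**Persisting complaints would still be seen.** Clinical assessments at 2 weeks, 1 month and 3 months and the medication reviews (section 9.1.6) would leave traces. They would not create an AE record or the duty to follow it up.

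**Conclusion.** The point holds in a limited form. As written, a Table 9 event that still fits its description, starts inside its window and then persists or needs treatment is not required to enter the AE data. For one that meets a seriousness criterion, 11.2.2 conflicts with 11.1 and Table 6.

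The size cannot be stated, because the documents give no frequency for such events. A reader might put it at 1/50 = 2 percentage points of AE incidence per missed case. That holds only if the denominator is the roughly 50 treated subjects and the affected subject has no other reported AE. The SAP fixes no denominator for the AE tables, so the documents do not support the figure as a general statement.

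The efficacy comparison, the composite and the other safety endpoints are untouched. The conclusion assumes that sites apply the onset sentence literally. A site that reads the column heading as ending the exemption would report more, and that would produce inconsistent recording between sites. This is a cheap improvement to AE capture.

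**What to change.** In section 11.2.2, replace the onset sentence with a rule on the whole course of the event. A Table 9 event is exempt only if it is non-serious, starts and resolves within the stated time frame, and needs no treatment beyond routine post-procedure care. Any other Table 9 event is reported as an AE with its true onset date. The opening line of the list should be made subject to this rule, so that 11.2.2 no longer contradicts the AE and SAE definitions in 11.1 or the reporting duty in Table 6.

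The CRF completion guidance needs the same wording. The change concerns recording only and alters no clinical management or endpoint. The cost is one sentence in the protocol, the matching guidance and a few more AE forms.

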**Table 9: Unavoidable Adverse Events**

Event Description	Time Frame (hours) from the Renal Denervation Procedure
Anesthesia related nausea/vomiting	24
Low grade fever (<100°F or <37.8°C)	48
Mild to moderate bruising/ecchymosis (at insertion site)	168
Sleep problems (insomnia)	72
Back pain related to laying on table	72
Elevated blood pressure	During the procedure

### ***11.2.3. Unanticipated Adverse Device Effect***

Medtronic will conduct an evaluation of the unanticipated adverse device effect (UADE) in accordance with 21 CFR 812.46(b) and shall report the results of such evaluation to US FDA and to all reviewing ethics committees and participating investigators within 10 working days after Medtronic first receives notice of the effect. Thereafter, Medtronic shall submit such additional reports concerning the effect as FDA requests. Events reported for this study from all geographies will be reviewed and assessed for UADE reporting to the FDA. Events deemed to be UADEs will be submitted per local reporting requirements

### ***11.2.4. Device Deficiencies***

All device deficiencies and malfunctions will be documented on the appropriate CRF, reported to Medtronic, and reported to the EC/IRB (if required) within the EC/IRB required timeframe and local and national regulations. Device deficiencies that did not lead to an adverse event should be reported on a device deficiency form, one for each device deficiency. Please refer to the device deficiency CRF for the information to be reported for each device deficiency that did not lead to an adverse event. The device deficiency CRF must be “saved as Complete” in the remote data capture (RDC) system to ensure it is reported to Medtronic as soon as possible.

Device deficiency reporting requirements do not apply to the OBP or ABPM devices used within the study and will not be collected for these devices.

### ***11.2.5. Product Complaint Reporting***

Product complaint reporting and vigilance reporting are applicable, and AEs related to any market-released device during the study must be reported. Refer to local regulations for reporting requirements.

It is the responsibility of the investigator to report all product complaint(s) associated with a medical device distributed by Medtronic, regardless whether they are related to intended use, misuse, or abuse of the product. Reporting must be done immediately and via the regular channels for market-released products. The reporting of product complaints by the sponsor must be done according to the local standard operating procedures. Medtronic will notify the RAs (e.g. CA) as applicable for the following incidents immediately upon learning of them and is not limited to AEs and DDs only:

- Any malfunction or deterioration in the characteristics and/or performance of a device, as well as any inadequacy in the labeling or instructions for use which led or might have led to the death or serious deterioration in the state of health of a subject, user, or other person.
- Any technical or medical reason resulting in withdrawal of a device from the market by the manufacturer.
- Any serious deterioration in the state of health, including:
  - Life-threatening illness or injury,
  - Permanent impairment of a body function or permanent damage to a body structure,
  - A condition necessitating medical or surgical intervention to prevent permanent impairment of a body function or permanent damage to a body structure.

### ***11.2.6. Emergency Contact***

Investigators should contact their responsible Medtronic study representative if they have any questions regarding reportable AEs or device deficiencies. Sponsor contact information (including name, title, address, and telephone number(s)) is subject to change and will be maintained in a document separate from the CIP and provided to sites.

For reportable AEs or device deficiencies that require immediate reporting (see **Table 6**), initial reporting shall be done by completing the appropriate CRF. If the CRF is not available, the reportable AE or device deficiency form in the Investigator Site File must be completed, signed, and dated by the principal investigator or his/her authorized designee(s), and submitted to the RS MC2 Safety Portfolio APV CRDN [[contact]](mailto:[contact]) email box or to the responsible Medtronic study representative. In due time, the AE or device deficiency needs to be entered in the CRF as well.

## 12. Data Review Committees

### 12.1. Clinical Event Committee

The clinical event committee (CEC) is composed of multiple clinicians with pertinent expertise who are not participants in the study and who do not have any other real or potential conflicts of interest. The CEC is charged with the development of specific criteria used for the categorization of clinical events and clinical endpoints in the study. Criteria will be established for selected complications and clinical events. At the onset of the study, the CEC will establish explicit rules outlining the minimum amount of data required, and the algorithm followed in order to classify a clinical event. The CEC will meet regularly to review and adjudicate pre-defined clinical endpoint events. If needed, the adjudication committee will require collection of additional source documentation from the clinical centers. The procedures by which the CEC will operate will be documented in a separate charter.

### 12.2. Data Safety Monitoring Board

The primary responsibility of the data safety monitoring board (DSMB) is to monitor the health, safety, and welfare of subjects. The DSMB will be composed of physicians who have experience in clinical studies in hypertension and/or cardiovascular indications and one biostatistician with experience in analysis of clinical trials. The members of the DSMB will not be investigators in the study and will be independent of Medtronic. Medtronic personnel may attend the meetings to answer questions but will not have a vote in determining the committee's recommendations.

Prior to the first DSMB review, guidelines for the identification, and evaluation of significant safety findings and/or increased frequency of events that may impact the rights, safety, or welfare of subjects will be established. All materials, discussions, and proceedings of the DSMB are completely confidential. The proceedings of each DSMB meeting will be recorded in minutes. The DSMB Chairperson will be responsible for providing a written recommendation regarding study conduct (e.g. continue as planned, specify a modification, or termination) to Medtronic and the study principal investigators. Additional details on the DSMB process, meeting, and data review schedule, as well as reporting expectations will be provided in the DSMB Charter.

### 12.3. Study Coordinating Investigators

The study coordinating investigators' (CI) role will be to provide overall supervision of the study, advise in study design, provide feedback on current practice and to assist in communications with clinical investigational sites in partnership with Medtronic. The study CIs will meet periodically by teleconference or in person to monitor the progress of the study, including subject enrollment, clinical site progress, and protocol compliance. The study coordinating investigators will also be responsible for reviewing the final results and determining the methods of presentation and publication together with Medtronic.

## 13. Statistical Design and Methods

### 13.1. General Methods

Descriptive statistics of continuous outcomes will be presented and include sample size, mean, standard deviation, median, interquartile range, minimum and maximum. For categorical outcomes, the number and percentage of subjects in each category will be presented. Paired t-tests will be used to compare changes in continuous measures from baseline to follow up. All statistical analyses will be performed using SAS for Windows (version 9.2 or higher) or other widely accepted statistical or graphical software. Subject data listings and tabular or graphical presentations of results will be provided, as applicable. Additional details on the analysis will be provided separately in the statistical analysis plan (SAP) for this study.

In accordance with the US FDA guidance document “FDA Guidance on Conduct of Clinical Trials of Medical Products during COVID-19 Pandemic” [8], additional analyses will be performed to assess the effect of the COVID-19 pandemic on the study outcomes as described in the statistical analysis plan.

### 13.2. Analysis Sets

#### 13.2.1. *Intention-To-Treat Population*

All enrolled subjects are included in the intention-to-treat (ITT) population. Subjects who meet the anti-hypertensive medication escape criteria ( $OSBP \geq 180$  mmHg or safety reasons) will be analyzed using last observation carried forward (LOCF) for their blood pressure measurements. More details on the algorithm can be found in the table specifications document. Safety outcomes, and office and ambulatory blood pressure outcomes out to three months will be presented for this population.

#### 13.2.2. *Modified Intention-To-Treat Population*

All enrolled subjects except subjects who meet the anti-hypertensive medication escape criteria ( $OSBP \geq 180$  mmHg or safety reasons) will be excluded from the modified ITT population. Office and ambulatory blood pressure outcomes out to three months will be presented for this population.

#### 13.2.3. *Per Protocol Population*

All treated subjects, meeting the following criteria are included in the per protocol population analysis::

1. Subjects showing medication compliance in blood and/or urine (via drug testing data) at Screening Visit 2 (SV2) and three months post-procedure.
2. Exclude subjects with protocol deviation code 101 (consent not obtained).

3. Exclude subjects who do not meet the following inclusion/exclusion criteria:

- Inclusion: Individual has an office systolic blood pressure (SBP)  $\geq 150$  mmHg and  $< 180$  mmHg and an office DBP  $\geq 90$  mmHg measured at Screening Visit 2, according to the guidelines in **Appendix 16.5** of the CIP.
- Inclusion: Individual has a 24-hour ABPM average SBP  $\geq 140$  and  $< 170$  mmHg measured at Screening Visit 2, according to guidelines in **Appendix 16.5** of the study protocol.
- Exclusion: Individual has undergone prior renal denervation.
- Exclusion: Individual has renal artery anatomy that is ineligible for treatment.
- Exclusion: Individual has one or more of the following conditions: stable or unstable angina within three months of enrollment, myocardial infarction within three months of enrollment; heart failure, cerebrovascular accident or transient ischemic attack, or atrial fibrillation at any time.

4. Exclude subjects meeting the anti-hypertensive medication escape criteria (OSBP  $> 180$  mmHg or safety reasons).

Office and ambulatory blood pressure outcomes out to three months will be presented for this population.

